### 8.4 Safety monitoring and stopping rule

This study will enroll the first 6 patients to the MSC arm for safety run in. Based on experience, we expect the toxicity of MSC is low about 5-10%. The chance of observing tSAEs in more than two out of six patients is 1.6%. After the first six patients complete safety monitoring at day 28, we will halt the study if more than two patients have tSAEs. Otherwise, the study will continue to enroll additional patients

The study will continuously monitor the safety of MSCs infusions in patients who are randomized to the MSC arm so that the accrual can be halted early if there is an unexpectedly high rate of treatment-related serious adverse events (tSAE) at day 28, defined in Section 7.4.5. Patients who don't complete the 28-day observation due to a reason other than tSAE will be deemed not evaluable for tSAE. However, those patients in the randomization phase are evaluable for efficacy and will not be replaced. A tSAE rate of greater than or equal to 25% is considered excessive. The occurrence of tSAEs will be monitored using a stopping guideline based on a Pocock-type boundary method [83]. The following sequential stopping boundaries will be used:

Number of Patients	1-3	4-5	6-7	8-9	10-12	13-14	15-17	18-20	21-23	24-26	27-28	29-30
Number of tSAEs <	-	4	5	6	7	8	9	10	11	12	13	14

The accrual will be halted if the number of tSAEs is equal to or exceeds the boundary in the above table. Under this sequential stopping rule, the probability of early stopping is 5% if the true tSAE rate is 25%, and the probability of early stopping will be high at 81% if the true tSAE rate is 50%.

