## **2 Study Design**

### **2.1 Study Overview**

This study is a single center open label, non-blinded randomized, controlled study designed to evaluate the use of single donor banked bone marrow derived MSCs versus standard of care as therapy for patients with ARDS due to COVID-19 disease. The study will first enroll and treat six patients with MSCs for safety run in. If no more than 2 treatment-related severe adverse events (tSAEs) are observed, the study will enroll and randomize additional 60 patients in a ratio of 1:1 to receive either MSCs or routine/supportive care.

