### **8.2 Sample size**

This early phase study will accrue a total of 66 patients with 6 patients for safety run in and additional 30 patients in each treatment arm by randomization. MSCs will be manufactured in our GMP facility and available to treat at least 36 patients. The study primary efficacy endpoint is improvement in clinical status at least two categories on a six-category ordinal scale at day 14 post randomization. The six-category ordinal scale ranges from 6 to 1 with a higher score indicates worse clinical outcome, i.e. 6 = death; 5 = hospitalization, requiring ECMO and/or IMV; 4 = hospitalization, requiring NIV and/or HFNC therapy; 3 = hospitalization, requiring supplemental oxygen (but not NIV/HFNC); 2 = hospitalization, not requiring supplemental oxygen; 1 = hospital discharge. The scale will be used to evaluate patients' status daily from baseline to day hospital discharge. Patients' clinical status at day 14 post randomization will be dichotomized as 'improved' (decreased by at least two categories) or 'not improved'. Patients who died before day 14 will be deemed as 'not improved'. Public data about the novel COVID-19 are limited and the data varies between all studies. Based on reported data, the time to improvement in patients with supportive care were about 22-23 days [20, 82] we expect 10% patients in the control group and 35%

patients in the MSC group will achieve 'improved' status at day 14, a total sample size of 66 (36 in the MSC arm and 30 in the control arm) will provide 84% power to detect a difference in clinical improvement of 25% between control (10%) and MSC (35%) at a 7.5% one-sided significance level using a Chi-square test.

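### The run-in halting count is read only once, after all six patients reach day 28, so no stated rule stops entry of further run-in patients once a third has a tSAE

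*Combined protocol and SAP*

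**What the plan says.** Section 2.1 describes the run-in: "The study will first enroll and treat six patients with MSCs for safety run in". Randomisation of 60 more patients follows on this condition: "If no more than 2 treatment-related severe adverse events (tSAEs) are observed". No earlier look is mentioned there.

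Section 8.4 sets the rule in terms of patients and fixes when it is read: "After the first six patients complete safety monitoring at day 28, we will halt the study if more than two patients have tSAEs". It gives an expected tSAE rate of 5–10% and a 1.6% chance that the run-in exceeds its limit.

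The next paragraph of 8.4 defines continuous monitoring and its population: "The study will continuously monitor the safety of MSCs infusions in patients who are randomized to the MSC arm". Its boundary table ends at 30 patients. Section 8.2 shows that 30 is the randomised MSC arm without the run-in: "6 patients for safety run in and additional 30 patients in each treatment arm by randomization".

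Other stopping provisions concern the individual. Section 5.3.2 stops an infusion in progress or bars further doses for that patient, and section 9.1 takes that patient off treatment. Section 10 refers to a monitoring board plan and an FDA-filed monitoring plan, whose contents are not in the document.

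**The concern.** A safety run-in exists to limit exposure while little is known about the product in this population. Here its only group-level rule is read when the sixth patient finishes day 28. Suppose patients 1, 2 and 3 each have a tSAE. The limit of two is already exceeded, and nothing seen in patients 4 to 6 can bring the count back down. Section 8.4 nevertheless gives no instruction until all six have been entered and followed.

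Several tSAE components in section 7.4.5 run on a short clock: thromboembolism within 48 hours of infusion, grade 4 events not resolving to grade 2 within 72 hours, and allergic reactions. The information could therefore be available weeks before the formal reading. At stake is the exposure of up to three further patients after the protocol's own criterion for halting has been met.

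**Working it through.** **Inputs.** Run-in of 6, all on MSC; halt if at least 3 patients have a tSAE; expected rate 5–10%; 25% or more considered excessive; 50% used by the plan as its high-rate scenario (all section 8.4). Randomised MSC arm of 30 (section 8.2). Patients are treated as independent with a common tSAE probability p.

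**Step 1: the plan's own figures.**

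Run-in: P(X ≥ 3) = 1 − Σ(k = 0 to 2) C(6,k) p^k (1−p)^(6−k). At p = 0.10 this is 1 − (0.53144 + 0.35429 + 0.09842) = 0.0159. The stated 1.6% therefore reproduces at the upper end of the expected range. At p = 0.05 it is 0.0022.

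Continuous boundary: an exact patient-by-patient recursion over 30 patients, stopping when the count equals or exceeds the tabulated value, gives 0.0489 at 25% and 0.8127 at 50%. The plan states 5% and 81%. These reproduce over 30 patients without the run-in, which agrees with the wording that confines this rule to randomised patients.

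**Step 2: when the third affected patient appears.** The documents state no interval between run-in patients. Assume they enter one at a time, with each outcome known before the next entry. The probability that patient k is the third with a tSAE is

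P(k) = C(k−1, 2) p³ (1−p)^(k−3), for k = 3, 4, 5, 6.

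- Count passed with someone still to enter: P(3) + P(4) + P(5).
- Expected number entered after the count is passed: E = 3·P(3) + 2·P(4) + 1·P(5).
- Per failed run-in: divide each by P(X ≥ 3).

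| p | P(3) | P(4) | P(5) | P(6) | Run-in fails | Passed by patient 5 | Share of failures | E per run-in | E per failed run-in |
|---|---|---|---|---|---|---|---|---|---|
| 5% | 0.00013 | 0.00036 | 0.00068 | 0.00107 | 0.0022 | 0.0012 | 52% | 0.002 | 0.8 |
| 10% | 0.00100 | 0.00270 | 0.00486 | 0.00729 | 0.0159 | 0.0086 | 54% | 0.013 | 0.8 |
| 25% | 0.01562 | 0.03516 | 0.05273 | 0.06592 | 0.1694 | 0.1035 | 61% | 0.17 | 1.0 |
| 50% | 0.12500 | 0.18750 | 0.18750 | 0.15625 | 0.6563 | 0.5000 | 76% | 0.94 | 1.4 |

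Worked line at 25%: E = 3(0.01562) + 2(0.03516) + 0.05273 = 0.170, and 0.170 / 0.1694 = 1.0. These are patients, not infusions; section 5.3.1 allows a second infusion.

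**Step 3: does acting early alter the decision?** The four P(k) sum to P(X ≥ 3), so the set of run-ins that fail is the same whether the count is read as it accrues or at the end. The 1.6% is unchanged. Section 8.4 makes a patient non-evaluable only when day 28 is missed for a reason other than a tSAE, so a patient with a tSAE stays in the count.

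**Step 4: would extending the continuous table to the run-in be enough?** No. It has no boundary for patients 1–3, requires 4 tSAEs at 4–5 patients and 5 at 6–7. Of run-ins with at least 3 affected patients, 97%, 91% and 71% (p = 10%, 25%, 50%) would not cross it within the six.

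**The case against.** The strongest reply is that silence is not an instruction. Section 8.4 fixes when the formal gate is read and does not forbid earlier action. Section 10 places the trial under two monitoring plans, and section 7.4.3 routes serious events through an SOP; any of these might lead to a pause. A reader might infer that the protocol requires dosing to go on after a third tSAE. The documents do not support that: they only contain no rule that stops entry. That narrower statement stands, because the unseen plans put no rule into section 8.4, where the trial's stopping rules are set out.

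A reader might also infer that the run-in is less well protected than the randomised phase. That is true of timing only. The run-in count is the stricter one: within six patients it halts with probability 16.9% at a 25% rate and 65.6% at 50%, against 1.6% and 18.8% for the continuous table. Three tSAEs in the first three randomised MSC patients would not trigger the table either.

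Two further objections limit the point. Attribution can change: section 7.4.5 asks for alternative causes, including COVID-19 itself, to be weighed, so the count is settled only once attribution is final. And the size rests on strictly sequential entry; with overlapping enrolment the saving could approach zero, although it cannot be negative.

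**Conclusion.** The point holds as a gap in the timing and coverage of the run-in rule. No stated figure is wrong: the 1.6%, 5% and 81% all reproduce. Between the third confirmed tSAE and the sixth patient's day 28, no rule in the documents stops further entry to the run-in, although the halting criterion has been met.

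If the expected 5–10% rate is right, the situation is rare (0.1–0.9%). A run-in is there for the case where that expectation is wrong. At 25% the chance is 10%, with 0.17 patients per run-in entered after the count is passed; at 50% it is 50%, with 0.94 patients. The maximum is three. These figures assume sequential entry with each outcome known before the next, independent patients with a common tSAE rate, and final attribution when an event is counted. The change is worth making because it cannot increase exposure and leaves the go/no-go rule as it is.

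**What to change.** In section 8.4, state that the existing run-in count is read as tSAEs accrue: accrual to the run-in is halted as soon as a third patient has a confirmed tSAE, and otherwise the go/no-go decision is made when the sixth patient completes day 28. Keep the threshold and the 1.6%. How second infusions in patients already treated are handled at that point is for the sponsor to decide and state.

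In the same edit, reconcile section 2.1, which limits the number of tSAE events, with section 8.4, which limits the number of patients with tSAEs. One patient with several events would be counted differently under the two.

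Cost: one sentence in 8.4 and a wording correction in 2.1, with no change to sample size, threshold or error rate.

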### **7.4 Drug Toxicity and/or Adverse Reactions**

- 7.4.1.** For consistency, toxicity for all patients will be evaluated using the NCI Common Toxicity Criteria scale (version 5.X; <http://ctep.cancer.gov>).
- 7.4.2.** Adverse events will be collected as per SOP [J02.05.XX](#) and [J02.75.XX](#). Data on all new adverse experiences/toxicities (regardless of seriousness) and worsening of baseline toxicities by at least one grade following infusion will be collected for documentation purposes for 4 weeks after the last dosing of the study drug/biologic with the exception of all toxicities which were deemed to be related to the MSC infusion, which will be followed until resolved.
- 7.4.3.** Serious Adverse event data will be collected and reported as per SOP J02.06.XX until 28 days after the last dosing of study drug/biologic or until time of discharge, whichever comes first, and should consist of both solicited and volunteered events reported by the patient.
- 7.4.4.** Infusion/allergic reactions will be evaluated by continuous monitoring the patient's vital signs from the time of administration until two hours after starting the infusion.
- 7.4.5.** Treatment-related serious adverse events (tSAE) will be considered as those directly related to the investigational infusion product. Adverse event grading

will be as defined by the NCI Common Terminology Criteria for Adverse Events (CTCAE), Version 5. In making this assessment, there should be consideration of the probability of an alternative cause (for example, COVID-19 itself or some other condition preceding randomization) and the timing of the event with respect to study treatment. The safety endpoint of the study is tSAE, defined as:

- Any grade 5 AE
- Any grade 4 AE that fails to return to grade 2 within 72 hours post-infusion
- Grade 2 to 4 allergic reactions (severe rash, bronchospasm, and immediate-type allergic reactions)
- Arterial or venous thromboembolic event occurring within 48 hours of infusion
- Serious Adverse Event (SAE) that, in the treating physicians' judgment, is considered related to MSC infusion and requires withdrawal from the study

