### 8.5 Statistical Analysis

All patients who received any MSC infusions in the MSCs arm or supportive care in the control arm will be included in the safety analyses. All efficacy analysis will be based on the intent to treat (ITT) population, defined as eligible and randomized subjects.

Adverse event data and corresponding toxicity grades after treatment will be summarized descriptively by treatment arms. All adverse events, grades, and attributions

will be listed and tabulated. Toxicity information including the type, severity, time of onset, time of resolution, and the probable association with the study regimen will be tabulated and summarized by treatment arms. Rate of tSAEs in patients treated with MSCs will be reported as proportion and its 95% confidence interval overall and by cancer status (cancer patients versus non-oncologic patients).

Clinical outcome data (increase in oxygen saturation, decrease in oxygen supplementation, progression to mechanical ventilation or ECMO, evolution of other end-organ damage, severity of ARDS, mortality rate, cause of death, duration on ventilation, durations of ICU stay and hospital stay, duration of vasopressor use, negative SARS-Co-V-2 RT-PCR by day 28, and change in disease severity scores and corticosteroid use) will be summarized descriptively. Categorical variables will be summarized by frequencies and percentages. Continuous variables will be summarized by means, standard deviations, medians, interquartile ranges.

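### Sections 8.4 and 7.4.3 conflict with Sections 8.5, 7.4.2, 7.3.1 and the study calendar on who counts toward the tSAE rate and how long serious events are collected

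*Combined protocol and SAP*

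**What the plan says.** **Endpoint and monitoring.** Sections 2.3.1 and 8.1 make tSAE the primary safety endpoint. Section 8.4 monitors it at day 28 in the randomized MSC arm with a Pocock-type boundary, calls a rate of 25% or more excessive, and states halting probabilities of 5% at a true 25% rate and 81% at 50%.

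**Denominator.** Section 8.4 says that patients who do not "complete the 28-day observation due to a reason other than tSAE will be deemed not evaluable for tSAE". It adds that "those patients in the randomization phase are evaluable for efficacy and will not be replaced". Section 8.5 sets no completion condition: "All patients who received any MSC infusions in the MSCs arm or supportive care in the control arm will be included" in the safety analyses, and "Rate of tSAEs in patients treated with MSCs will be reported as proportion and its 95% confidence interval overall".

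**Collection window.** Section 7.4.3 collects SAE data "until 28 days after the last dosing of study drug/biologic or until time of discharge, whichever comes first". Section 7.4.2 says that adverse event data, serious or not, "will be collected for documentation purposes for 4 weeks after the last dosing of the study drug/biologic", and follows toxicities related to the infusion until they resolve. Section 7.3.1 keeps contact with discharged patients through day 28, in clinic or by telephone. The calendar's adverse event row runs from day 0 to day 28 without the footnote that limits other rows to inpatients.

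**Definition.** Section 7.4.5 first ties a tSAE to a direct relation with the product. Its list then includes every grade 5 event, with no attribution condition in that bullet. Other components are tied to the infusion, to 48 hours (thromboembolism) or to 72 hours (grade 4 events that do not resolve).

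**The concern.** Which denominator applies is left open, and the choice is not neutral. On the ordinary reading of Section 8.4, a patient with a tSAE stays in and only event-free patients leave, so exclusion can only raise the proportion. Section 1.3 cites mortality approaching 50% in COVID-19 ARDS. If a COVID-19 death is a non-tSAE reason for not completing, many treated patients could leave, although the 48- and 72-hour components had usually been observed in full.

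The collection window pushes the other way. A clause that ends SAE collection at discharge can lose late related SAEs and deaths, which lowers the numerator. The shortest window is thus applied to the most serious events. The two effects have unknown sizes and cannot be assumed to cancel. Two sites following different sentences of this protocol would report different primary safety rates, and the halting rule would not behave as Section 8.4 states.

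**Working it through.** **Inputs.** From Section 8.4, halt when the number of tSAEs reaches b(n): 4 at n = 4-5, 5 at 6-7, 6 at 8-9, 7 at 10-12, 8 at 13-14, 9 at 15-17, 10 at 18-20, 11 at 21-23, 12 at 24-26, 13 at 27-28, 14 at 29-30. From Section 8.2, 36 MSC patients (6 run-in, 30 randomized). The documents give neither the number of non-completers nor the share of tSAEs after discharge, so both are assumed ranges.

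**1. The plan's own figures.** Take patients one at a time. From n patients and k events, move to (n+1, k+1) with probability p and to (n+1, k) with probability 1-p, and stop when k ≥ b(n). With 30 evaluable patients the halting probability is 4.9% at p = 0.25 (stated 5%) and 81.3% at p = 0.50 (stated 81%). Both reproduce.

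**2. Events missed after discharge.** If a share f is missed, the observed rate is p(1-f).

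| f | true 50% appears as | halting probability | true 25% appears as |
|---|---|---|---|
| 0 | 50% | 81% | 25% |
| 10% | 45% | 65% | 22.5% |
| 20% | 40% | 45% | 20% |
| 30% | 35% | 26% | 17.5% |

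**3. Event-free patients removed.** Infuse 30 patients and let each event-free patient become non-evaluable with probability d. Each infused patient now moves the state to (n+1, k+1) with probability p, to (n+1, k) with probability (1-p)(1-d), or leaves it unchanged with probability (1-p)d. The rate among evaluable patients is p / [p + (1-p)(1-d)].

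| d | rate among evaluable at p = 0.25 | halting probability |
|---|---|---|
| 0 | 25% | 4.9% |
| 20% | 0.25/0.85 = 29.4% | 10% |
| 40% | 0.25/0.70 = 35.7% | 21% |
| 50% | 0.25/0.625 = 40.0% | 30% |

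At a true 10% rate, the top of the range the plan expects, the same calculation gives 0.06% at d = 0 and 0.8% at d = 50%.

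**4. The reported rate.** Assume 6 tSAEs among 36 treated: 6/36 = 16.7% (Clopper-Pearson 95% CI 6.4-32.8%). Removing 20%, 40% or 50% of the 30 event-free patients takes out 6, 12 or 15, giving 6/30 = 20%, 6/24 = 25% or 6/21 = 28.6%. The same six events thus fall below, on or above the plan's 25% mark.

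**5. Deaths.** If deaths judged unrelated are not tSAEs, step 3 applies. If the grade 5 bullet is read literally, those deaths are tSAEs and stay in. Deaths alone at 40% or 50% would then carry a halting probability of 45% or 81% by the recursion in step 1, whatever the product does.

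**The case against.** The strongest reply is that the final analysis is already right. Section 8.5 covers every treated patient, and the evaluability sentence stands only in the monitoring section. That has force. A reader might infer that the primary safety rate is definitely computed on a selected subset; the documents do not support that. What they show is an unresolved conflict between Sections 8.4 and 8.5. For the boundary itself, however, Section 8.4 is the only text.

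A reader might also infer that a patient discharged early has no serious events recorded for the rest of the 28 days. Section 7.4.2, the post-discharge contacts and the calendar row say otherwise, so this is a conflict of wording, not a proven gap. Components tied to the infusion or to 48-72 hours are little affected. Nor do controls lack an event window: Section 7 sets their day 0 at randomization, and the calendar row is not limited to the MSC arm. Only the wording of Sections 7.4.2 and 7.4.3 is tied to dosing.

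On size, exclusion changes the patient count and not the event count. With few events no decision moves: 3 tSAEs are far below 9 at n = 15 and 14 at n = 30. The plan calls 25% excessive, so extra halting there is in the cautious direction, and at 10% it stays below 1%. This limits the harm but does not restore the stated 5%.

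Finally, Section 8.4 does not say outright that a patient with a recorded tSAE who later dies of another cause stays counted. If non-completion removed patients regardless of tSAE status, 24, 18 or 15 evaluable patients would give a halting probability at a true 50% rate of 73%, 58% or 49%. The direction changes, and the stated figure still fails.

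**Conclusion.** The concern holds as a set of conflicts to be resolved, not as a demonstrated net bias. The discharge clause in Section 7.4.3 contradicts the day-28 endpoint; if 10-30% of tSAEs were missed, the halting probability at a true 50% rate would fall from 81% to 65-26%. The evaluability rule in Section 8.4 contradicts Section 8.5; if 20-50% of event-free patients dropped out, the halting probability at a true 25% rate would rise from 5% to about 10-30%, and the evaluable-only rate would be too high. Both ranges are assumptions, and the second takes it that patients with a tSAE stay counted and that deaths judged unrelated are not tSAEs. Section 7.4.5 leaves that last point open, and it matters most. The difference in window wording between arms is minor.

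**What to change.** 1. **Section 7.4.3:** delete the alternative that ends SAE collection at discharge, and ask about SAEs at the clinic or telephone contacts that Section 7.3.1 and the calendar already schedule at days 14, 21 and 28. Cost: a few more SAE reports.
2. **Section 8.4:** use all infused patients for both the reported tSAE rate and the boundary, as Section 8.5 implies. Patients who die of a cause judged unrelated stay in the denominator. Add an evaluable-only sensitivity analysis, because counting early dropouts as event-free treats unobserved time as safe and makes halting a little harder (9 tSAEs halt at 15-17 patients but not at 18 or more).
3. **Section 7.4.5:** reconcile the grade 5 bullet with the attribution requirement above it, so that the status of unrelated deaths is explicit before data accrue.
4. **Sections 7.4.2-7.4.3 (minor):** align the windows with the calendar's day 0-28 row in both arms, with day 0 at infusion for MSC and run-in patients and at randomization for controls. A window counted from randomization would not fit the six non-randomized run-in patients. A second infusion on day 3-5 extends a last-dose window to day 31-33 (3 + 28 to 5 + 28); list events in those extra days separately.

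Apart from the extra SAE reports and one added sensitivity analysis, these are wording changes, with no new visits.
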